2.1.1 General definitions

2.1.1.1 Study drug and study treatment:

Study drug is defined as alpelisib.

Study treatment is defined as alpelisib plus fulvestrant.

2.1.1.2 Date of first administration of study drug/treatment

The date of first administration of study drug is defined as the first date when a nonzero dose of study drug is administered and recorded on the Dose Administration Record (DAR) eCRF/eDiary. The date of first administration of study drug will also be referred to as start of study drug. Similar definitions apply for the other components of study treatment.

The date of first administration of study treatment is defined as the first date when a nonzero dose of any component of study treatment is administered and recorded on the DAR eCRF/eDiary. The date of first administration of study treatment will also be referred to as the start of study treatment.

2.1.1.3 Date of last administration of study drug/treatment

The date of last administration of study drug is defined as the last date when a nonzero dose of study drug is administered and recorded on the DAR eCRF. Similar definitions apply for the other components of study treatment.

The date of last administration of study treatment is defined as the last date when a nonzero dose of any component of study treatment was administered and recorded on the DAR eCRF.

2.1.1.4 Study day

Study day on first study drug intake date is 1.

The study day will be calculated as:

The date of the event (visit date, onset date of an event, assessment date etc.) – reference start date + 1 if event is on or after the reference start date;

The date of the event (visit date, onset date of an event, assessment date etc.) – reference start date if event precedes the reference start date.

The reference start date for safety assessments (e.g., adverse event onset, laboratory abnormality occurrence, vital sign measurement, dose interruption etc.) is the start of study treatment. (Note: if an adverse event starts before the start of study treatment the study day displayed on the listing will be negative).

The reference start date for all other, non-safety assessments (e.g., tumor assessment, death, disease progression, tumor response, and patient reported outcomes (PRO)) is the start of study treatment. In other words, all efficacy time -to-event variables (e.g., progression-free survival) will be calculated from start of study treatment.

2.1.1.5 Baseline

For efficacy evaluations, the last available assessment on or before start date of study treatment will be used as the “baseline” value or “baseline” assessment. In the context of baseline definition, the efficacy evaluations also include ECOG performance status and patient-reported outcomes. For RECIST based endpoint PFS, within 28 days prior to start of trial treatment (Day -28 to Day -1 prior to Cycle 1, Day 1). A window of 28 days from the start of study treatment will be allowed, i.e., the investigators will be maintained and baseline considered valid if the baseline assessment is within 28 days of treatment start date.

For safety evaluations (e.g., laboratory assessments and ECG), the last available assessment before or at date of start of study treatment will be used as the ‘baseline’ assessment.

Assessments specified to be collected post-dose on the first date of treatment are not considered as baseline values.

If patients have no value as defined above, the baseline results will be considered missing.

2.1.1.6 On-treatment assessment/event

Safety summaries and selected summaries of deaths will summarize only on-treatment assessments/events. An on-treatment assessment/event is defined as any assessment/event in the following time interval:

[date of first administration of study treatment, date of last administration of study treatment + 30 days], i.e., including the lower and upper limits. (Note: However, the calculation of study treatment duration will use different rules as specified in [Section 2.3.2.5](#)).

An AE started in the screening phase and ongoing in the on-treatment phase will not be considered as an on-treatment AE unless it has worsened.

If the last date of study treatment is missing, any assessment/event occurring after the start of study treatment will be considered as on-treatment.

Data listings will include all assessments/events, flagging those which are not on-treatment.

Note: The date of first administration of study treatment and the date of last administration of study treatment are defined in [Sections 2.1.1.2](#) and [2.1.1.3](#), respectively.

2.2 Analysis sets

Enrolled Set: The enrolled set consists of all patients who signed the informed consent.

Full Analysis Set: The Full Analysis Set (FAS) consists of all enrolled set patients who received at least one dose of any component of study treatment.

Safety Set: The Safety Set consists of all enrolled set patients who received at least one dose of any component of study treatment and have at least one post-baseline safety assessment.

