12.1 Analysis sets

The Full Analysis Set (FAS) comprises all participants that received any trial treatment.

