12.5.4 Safety endpoints

The safety endpoint will be type, frequency and severity (incidence proportion) of AESIs per CTCAE v4.03. In addition, a separate summary for death will be provided.

Adverse events

The number (and percentage) of participants with treatment emergent AEs (events started after the first dose of trial medication or events present prior to start of treatment but increased in severity based on preferred term) will be summarized in the following ways:

- by primary SOC and PT
- by primary SOC, PT and maximum severity
- by PT

Separate summaries will be provided for trial medication related AEs, death, SAEs, other significant AEs leading to discontinuation.

A participant with multiple AEs within a primary SOC is only counted once towards the total of the primary SOC.

Summary tables for AEs will include only AEs that started or worsened during the on-treatment period, the treatment-emergent AEs.

The incidence of treatment-emergent AEs (new or worsening from baseline) will be summarized by SOC and or PT, severity (based on CTCAE grades), type of AE, and relationship to trial treatment.

SAEs, non-serious AEs and AESIs during the on-treatment period will be tabulated.

All deaths (on-treatment and post-treatment) will be summarized.

All AEs, deaths, and SAEs will be listed.

Vital signs

All vital signs data will be listed by treatment group, participant, and visit/time and if ranges are available, abnormalities (and relevant orthostatic changes) will be flagged. Summary statistics will be provided by treatment and visit/time.

Clinical laboratory evaluations

All laboratory data will be listed by participant and visit/time, and if normal ranges are available abnormalities will be flagged. Summary statistics will be provided by visit/time. Shift tables using the low/normal/high/ (low and high) classification will be used to compare baseline to the worst on-treatment value.

Grading of laboratory values will be assigned programmatically as per NCI CTCAE version 4.03. The calculation of CTCAE grades will be based on the observed laboratory values only, clinical assessments will not be taken into account. CTCAE Grade 0 will be assigned for all non-missing values not graded as 1 or higher. Grade 5 will not be used. For laboratory tests where grades are not defined by CTCAE version 4.03, results will be categorized as low/normal/high based on laboratory normal ranges.

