2.3.2.5 Study treatment

Duration of study treatment exposure, cumulative dose, dose intensity (DI) and relative dose intensity (RDI) will be summarized. The number of patients with dose reductions/interruptions, and the reasons, will be summarized and listed. Details of the derivations and summaries are provided in the following sections.

The safety set will be used for all summaries and listings of study treatment.

Duration of study treatment exposure

The duration of exposure to study treatment will be calculated as Duration of exposure to study treatment (days) = (last date of exposure to any study treatment component) – (date of first administration of study treatment) + 1.

Duration of exposure to alpelisib (days) = (last date of exposure to alpelisib) – (date of first administration to alpelisib) + 1.

Duration of exposure to fulvestrant (days) = (last date of exposure to fulvestrant) – (date of first administration to fulvestrant) + 1.

The last date of exposure is defined as follows for the study treatment components:

For alpelisib: the last date of exposure is defined as the date of last administration of the corresponding medication;

For fulvestrant, the last date of exposure is defined as following:

If patient discontinues fulvestrant before C2D1 dose, then:

- Last date of exposure = last date of administration + 13 days.

If patient died or lost to follow-up within last date of administration + 13 days,

- then last date of exposure is date of death or last contact date, respectively.

If patient discontinues fulvestrant after C2D1 dose, then:

- Last date of exposure = last date of administration + 27 days.

If patient died or lost to follow-up within last date of administration + 27 days,

- then last date of exposure is date of death or last contact date, respectively.

The duration of exposure includes the periods of temporary interruption (of any component of the study treatment for any reason). The duration of study treatment exposure will be summarized. In addition, the duration of exposure to study treatment will be

categorized into time intervals (. < 1 month, 1- 2 months, 2 to 3 months, 3 to 4 months, 4 to 6 months, 6 to 8 months, 8 to 10 months and \geq 10 months); frequency counts and percentages will be presented for the number of patients in each interval.

Cumulative dose and average daily dose

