2.3.3 Prior, concomitant and post therapies

Prior anti-neoplastic therapy

Any prior anti-neoplastic medications, radiotherapy or surgery (biopsy and non-biopsy separately) will be listed for each patient.

Separate listings will be produced for prior anti-neoplastic medications, radiotherapy, and surgery.

Concomitant therapy

Concomitant therapy is defined as all interventions (therapeutic treatments and procedures) besides the study treatment that were administered to a patient, coinciding with the study assessment period (even if started before the study assessment period).

Concomitant medications will be coded using the World Health Organization (WHO) Drug Reference Listing (DRL) dictionary that employs the WHO Anatomical Therapeutic Chemical (ATC) classification system.

All concomitant therapies will be listed. Any concomitant therapies starting and ending prior to the start of study treatment or starting more than 30 days after the last date of study treatment will be flagged in the listing. The safety set will be used for all concomitant medication tables and listings.

Any anti-neoplastic therapy administered concomitantly with study treatment will be listed. .

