2.6 Safety analyses

The assessment of safety will be based mainly on the frequency of adverse events and on the number of laboratory/ECG values that fall outside of pre-determined ranges. Other safety data (e.g., vital signs and special tests) will be considered as appropriate.

All safety outputs will use the safety set. The safety summary tables will include 'on -treatment' events/assessments, i.e., those collected on or after the first date of study treatment and collected no later than 30 days after the date of last study treatment administration. The AEs started before the first dose but worsening during the treatment period are also considered as 'on - treatment' events. All safety events/assessments will be listed and those collected outside of the on treatment window will be flagged.

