2.6.2 Deaths

All deaths will be listed.

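### The SAP Safety Set adds an undeclared post-dosing condition, so a treated participant with no safety record after dosing could be left out of the safety and exposure listings

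*SAP*

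**What the plan says.** Protocol 12.1 has one analysis set: "The Full Analysis Set (FAS) comprises all participants that received any trial treatment". SAP 2.2 keeps it in equivalent terms: "The Full Analysis Set (FAS) consists of all enrolled set patients who received at least one dose of any component of study treatment". The SAP then adds a Safety Set that the protocol does not have, made up of enrolled participants who "received at least one dose of any component of study treatment and have at least one post-baseline safety assessment".

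That second set carries much of the report:

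- SAP 2.6: "All safety outputs will use the safety set".
- SAP 2.3.2.5, to which the compliance endpoint is also referred: "The safety set will be used for all summaries and listings of study treatment".
- SAP 2.3.3: "The safety set will be used for all concomitant medication tables and listings".

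On deaths, Protocol 12.5.4 says "All deaths (on-treatment and post-treatment) will be summarized". SAP 2.6.2, which sits inside the safety section, says "All deaths will be listed".

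SAP Section 4, the place for changes from the protocol's analyses, is marked not applicable. SAP Section 1 explains that enrolment was very low, the trial stopped early, and data will only be listed. SAP 2.6.1 nevertheless still describes adverse event tables.

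**The concern.** A safety population is normally fixed by exposure. Here membership also depends on what is recorded after exposure, so a treated participant about whom no safety information came back can be removed because that information is absent. The trial asks whether patients can be managed safely at a distance, and a treated participant with no safety follow-up is relevant to that question.

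The condition is also undeclared and loosely worded. Nothing in SAP 2.2 says what counts as a safety assessment, so membership in a borderline case would be settled at analysis. The death listing is caught between two instructions: the general rule of SAP 2.6 restricts it to the Safety Set, while SAP 2.6.2 promises every death.

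**Working it through.** The plan gives no power calculation or derived figure to reproduce; the planned number of about 20 rests on feasibility (Protocol 12.8, SAP Section 3). The check is mainly textual, followed by simple proportions.

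**1. Do the two definitions differ?** Yes. Protocol 12.1 and the SAP's FAS require dosing. The Safety Set requires dosing and a safety assessment after baseline. SAP Table 5-1 does not mirror this: the only deviation that removes a participant from safety analyses alone is not having been given study medication.

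**2. What would satisfy the extra condition?**
- SAP 2.1.1.5 treats safety assessments up to and including the treatment start date as baseline, apart from those specified as post-dose. Routine Cycle 1 Day 1 work therefore does not qualify.
- SAP 2.1.1.4, in setting reference dates for study day, names adverse event onset, laboratory abnormalities, vital signs and dose interruptions as examples of safety assessments. It puts death and disease progression with the non-safety assessments.
- Protocol Table 8-4 schedules daily home glucose readings from Day 2 to Day 14 of Cycle 1 within the laboratory plan. Table 8-1 has adverse events collected continuously.

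**3. Who can fall out?** Participants with a post-dose adverse event, home glucose reading or laboratory value would normally be in. What remains is a participant lost straight after the first dose, or a death with no adverse event recorded and no other safety record after dosing.

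**4. Where would that participant still be seen?**
- Disposition (SAP 2.3.1) and the visit listings, including unscheduled in-clinic visits for safety reasons (SAP 2.5.1): Enrolled Set.
- PFS, in which death is an event (SAP 2.5.2), and the PRO listings (SAP 2.9): FAS.
- The listing of discontinuations related to adverse events (SAP 2.5.1): no set stated.
- Exposure, compliance, concomitant medication, adverse event and laboratory outputs: Safety Set, so absent. The death listing is absent too if SAP 2.6 is read literally.

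**5. Size.** The number excluded is an assumption, since the documents do not say that any such participant exists. Rate = events / set size, with exact (Clopper-Pearson) 95% intervals for the death example.

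| Illustration at 20 treated | All treated | Safety Set |
|---|---|---|
| AE in 10 participants, 1 other excluded | 10/20 = 50.0% | 10/19 = 52.6% |
| AE in 10 participants, 2 others excluded | 10/20 = 50.0% | 10/18 = 55.6% |
| 1 death with no recorded AE, excluded | 1/20 = 5.0% (0.1 to 24.9) | 0/19 = 0% (0 to 17.6) |

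The first two rows change only the denominator, because the excluded person has no adverse event to lose. The third row applies only if a death rate is formed on this set.

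The documents reviewed do not give the number actually treated. At an assumed 10, 5 or 3, one omitted participant is 1/10 = 10%, 1/5 = 20% or 1/3 = 33% of those treated.

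**The case against.** The strongest reply is that the condition will hardly ever bite. Daily home glucose readings start on Day 2, and Protocol 8.4 counts glucose monitoring among its safety measures. Adverse events are collected throughout. Early discontinuers are called to an end-of-trial visit and, failing that, investigators are to seek safety follow-up (Protocol Section 8). A fatal adverse event is recorded as an adverse event with that outcome (SAP 5.2). The statements that all deaths, all adverse events and all safety events will be listed can also be read as overriding the general sentence in SAP 2.6. With listings only, no rate is affected.

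Most of this stands, and it rules out three stronger readings that a reader might infer:

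- *Adverse event withdrawals would vanish.* Not supported. SAP 2.1.1.4 names adverse event onset as a safety assessment, so a participant withdrawn for a post-dose event qualifies for the set.
- *The wait for the Day 15 nurse visit, or for the Cycle 2 Day 1 blood panel, is a window in which people drop out of the set.* Not supported. The condition asks for a safety assessment, not a visit or a full panel, and home glucose and event reporting come earlier.
- *An early death or dropout would disappear from the report.* Not supported, because disposition, visit, PFS and PRO outputs use wider sets.

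What the reply does not do is justify the condition. If every treated participant meets it, it has no effect; if one does not, it removes a treated person from the exposure and safety outputs. The examples in SAP 2.1.1.4 serve the study-day calculation and do not define set membership, so the wording remains open. The conflict over the death listing also remains.

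**Conclusion.** The point holds as a minor one. SAP 2.2 adds a condition that the protocol lacks, SAP Section 4 does not declare it, and three SAP sections apply it to all study-treatment, concomitant-medication and safety outputs. The harm is possible rather than shown: a missing row for a treated participant in the listings now planned or, if the summaries were produced at about 20 treated, a shift such as 50.0% to 52.6%, or one death going from 1/20 to 0/19.

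This rests on three assumptions: that at least one treated participant has no safety record after dosing; that a death report alone does not count as a safety assessment, as the grouping in SAP 2.1.1.4 suggests; and, for the death listing, that the general rule in SAP 2.6 prevails over SAP 2.6.2. The first is probably rare. The documents do not support a higher severity.

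**What to change.** - In SAP 2.2, define the Safety Set by dosing alone, in the same terms as the FAS, and delete the post-baseline condition. The set then agrees with Protocol 12.1 and with Table 5-1, and no departure on this point needs declaring in Section 4.
- In SAP 2.6.2, state that deaths among all treated participants are listed.
- Show treated participants with no safety data after baseline as a separate count, so that the absence is visible.

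The cost is a few lines of SAP wording and one count. No new data are needed.

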2.2.1 Subgroup of interest

Not applicable

2.3 Patient disposition, demographics and other baseline characteristics

Enrollment by study sites and local oncology clinics will be summarized on enrolled set. The reasons for screen failure will also be summarized.

2.3.1 Patient disposition

Patient disposition for all patients will be summarized based on enrolled set.

- Number (%) of patients treated/untreated
- Number (%) of patients who are still on-treatment (based on the absence of the ‘End of treatment’ page)
- Number (%) of patients who discontinued study treatment (based on the ‘End of Treatment’ page)
- Reasons for study treatment discontinuation (based on ‘End of Treatment’ page).
- Number (%) of patients who enroll into 15 year follow up protocol

End of Screening Phase Disposition with subject status for all patients will be summarized based on enrolled set.

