8.1.2 Information to be collected on screening failures

Participants who sign an ICF and are subsequently found to be ineligible will be considered a screening failure. The following CRFs must be completed for a screen failure patient:

- Screening phase disposition page of CRF (including reason for not being started on treatment)
- Informed consent
- Inclusion/Exclusion criteria
- Demography
- AEs (only if the participant experienced a SAE during the screening period after signing the ICF (see [Section 10](#) “Safety monitoring and reporting” for SAE reporting details))
- Withdrawal of consent, if applicable
- Death, if applicable

No other data will be entered into the clinical database for participants who are screen failures.

Participants who sign an ICF and are considered eligible but fail to initiate treatment for any reason will be considered an early terminator. The reason for early termination should be captured on the appropriate disposition CRF.

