9.1 Discontinuation and completion

9.1.1 Trial treatment discontinuation and trial discontinuation

Discontinuation of trial treatment for a participant occurs when trial treatment is stopped earlier than the protocol planned duration and can be initiated by either the participant or the investigator. Participants who discontinue trial treatment will be prematurely withdrawn from the trial.

The investigator must discontinue trial treatment for a given participant if he/she believes that continuation would negatively impact the participant's well-being.

Trial treatment must be discontinued under the following circumstances:

- Participant/guardian decision
- Use of prohibited treatment as per recommendations in the prohibited treatment section
- Any situation in which trial participation might result in a safety risk to the participant

If discontinuation of trial treatment occurs, the investigator should make a reasonable effort to understand the primary reason for the participant's premature discontinuation of trial treatment and record this information.

Whenever possible, participants discontinued early for any reason, should be requested to complete the assessments planned in EOT visit.

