2.1 Data analysis general information

The data will be analyzed by Novartis according to the data analysis section 12 of the study protocol which is available in Appendix 16.1.1 of the CSR. Important information is given in the following sections and details are provided, as applicable, in Appendix 16.1.9 of the CSR.

Statistical analysis will be performed using Statistical Analysis System (SAS)® (SAS Institute, North Carolina), Version 9.4 or higher.

Summary statistics for continuous variables will generally include the number of patients (n), mean, standard deviation, minimum, lower quartile, median, upper quartile, and maximum. Summary statistics will also be presented graphically wherever applicable. For discrete (categorical or binary) variables, the number and percentage of patients in each category will be presented. 95% CIs presented will be 2-sided unless otherwise specified. No formal statistical testing of hypothesis are planned to be performed.

All statistical analyses will be performed under the direction of Novartis personnel. It is planned that the data from all centers that participate in this study will be used. Trial duration is planned to be 12 cycles of 28 days of treatment each. Cut-off date will be Last Patient Last Visit (LPLV) is scheduled as per trial.

The statistical results will be displayed using tables, figures and listings (TFLs). Listings will include all data collected in the eCRF. When dates are imputed, a flag should be provided to show that this is imputed rather than an actual date. In listings, the imputed dates are reported in their original format before imputation. In general, patient listings will be sorted by patient number and assessment date (and time), if applicable.

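### The disposition rule in SAP 2.3.1 has no row for participants who complete 12 cycles, and its treatment-status rows are not limited to treated participants

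*SAP*

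**What the plan says.** SAP 2.3.1 sets the population: "Patient disposition for all patients will be summarized based on enrolled set". SAP 2.2 defines that set: "The enrolled set consists of all patients who signed the informed consent". The rows that matter here are:

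- A split of the whole set by whether any treatment was given.
- A status row that depends on a CRF page being missing: "Number (%) of patients who are still on-treatment (based on the absence of the". The form it goes on to name is the one for End of Treatment.
- A second status row that depends on that same form being present, and that counts those participants as having discontinued. The reasons for stopping are tabulated from it as well.
- A row counting participants who enter a 15-year follow-up protocol.

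The same section adds a disposition summary for the end of the screening phase, and SAP 2.3 adds a summary of the reasons for screen failure.

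Four other places bear on how these rows work:

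- Protocol 6.1.3 plans treatment for 12 cycles of 28 days.
- Protocol 9.1.1 states: "Discontinuation of trial treatment for a participant occurs when trial treatment is stopped earlier than the protocol planned duration".
- Protocol 8.1.2 lists the forms completed for a screen failure and then says: "No other data will be entered into the clinical database for participants who are screen failures".
- SAP 2.1 fixes the time point: "Cut-off date will be Last Patient Last Visit (LPLV").

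SAP section 1 says that the trial ended early for low enrollment, that the data will only be listed, and that this amendment reflects the change. Section 2.3.1 nevertheless still asks for counts and percentages.

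**The concern.** The two status rows turn on one fact: whether a particular CRF page exists. That works when treatment is open-ended, the cut-off comes while some participants are still being dosed, and the table contains only treated people. None of those conditions is secured here. Treatment has a planned end, the cut-off is the last visit of the last participant, and the table starts from consent.

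At stake is whether a basic table of the report is correct. This is a feasibility pilot that closed for slow enrollment. A reader will want to know who was screened out, who finished the planned treatment, who stopped early and why, and who stopped because the sponsor closed the trial. Protocol 12.5.3 also asks for the number of discontinuations and their reasons. A table that counts a completer as discontinued, or an untreated person as on treatment, answers those questions wrongly.

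**Working it through.** The plan gives no figure to reproduce on this point: there is no formal sample size calculation, and the rule is a classification. The check is to apply the rule as written to each kind of person in the Enrolled Set at the planned cut-off.

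| Person | End of Treatment page? | Treated/untreated row | Status row under SAP 2.3.1 | Correct status at LPLV |
|---|---|---|---|---|
| Screen failure | No; not among the forms in Protocol 8.1.2 | Untreated | Still on treatment | Never treated |
| Eligible, never dosed | Unknown; Protocol 8.1.2 names only an appropriate disposition form | Untreated | Cannot be determined | Never treated |
| Stopped before 12 cycles | Yes, if the page is filed as the SAP intends | Treated | Discontinued | Discontinued |
| Completed 12 cycles, page filed | Yes | Treated | Discontinued | Completed |
| Completed 12 cycles, no page filed | No | Treated | Still on treatment | Completed |

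Write S for screen failures, D for early stoppers, Cp for completers with the page and Cn for completers without it. Leave aside eligible people who were never dosed.

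- Still on treatment: the rule gives S + Cn. The correct count at LPLV is 0, because every participant has had a last visit. The error is S + Cn.
- Discontinued: the rule gives D + Cp. Under Protocol 9.1.1 the correct count is D. The error is Cp.
- Completed: the rule has no such row. The correct count is Cp + Cn.

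Only one row in the table above is certain to be classified correctly: the early stopper with the page. The completer is misplaced whichever way the page is handled, so no convention for filing it repairs the table.

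S, D, Cp and Cn are not in the documents. The planned enrollment of about 20 cannot stand in for them, because SAP section 1 says that enrollment failed and the trial was closed.

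The 15-year row is a separate misfit. Protocol 9.2 follows participants to the EOT visit or an earlier terminating event, and the protocol describes no longer study for them to enter.

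**The case against.** The strongest reply is that the surrounding text contains most of the damage. Screen failures are counted as untreated in the first row, appear again in the screening-phase disposition, and have their reasons summarized under SAP 2.3. The word still presupposes that treatment began, so a sensible programmer would limit the row to treated participants. The CRF page, table shells and programming specifications are not in the documents; if the page offers completion as a reason, completers could be picked out in the reasons row. And with data to be listed only, the table may never be produced.

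Much of this stands. A reader might infer that screen failures vanish into the on-treatment count; they do not, because other outputs identify them. What remains is that one person can sit in two contradictory rows, and the SAP does not state the restriction that would prevent it. The reply on completers is weaker: a completion reason would still be tabulated under reasons for discontinuation, beneath a parent count that includes completers.

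Three further inferences are tempting and unsupported:

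- That the table would overstate discontinuation by a known, large amount. This needs the numbers of completers and screen failures, which are not given. Estimating completers by applying the 25.0% AE discontinuation cited in Protocol 1.1 would also be unsound: it refers to alpelisib alone, and SAP 2.3.2.5 allows for alpelisib stopping before fulvestrant.
- That the retention endpoint inherits the error. The current SAP 2.5.1 calculates no retention proportion, and nothing ties the endpoint's 3-, 6- and 12-month time points to this page rule. Nor is this the only on-treatment definition: SAP 2.1.1.6 sets a dose-date window for assessments and events.
- That eligible people who never start are also counted as on treatment. Protocol 8.1.2 does not say which disposition form they receive.

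**Conclusion.** The concern holds as a defect in a stated classification rule. It rests on the literal text of SAP 2.2 and 2.3.1 and Protocol 6.1.3, 8.1.2 and 9.1.1. The missing row for completers is the firmer half, since it fails whether or not the page is filed. The overlap between untreated and still on treatment is real but softer: the SAP's other rows reveal it, and careful programming could avoid it.

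The size cannot be stated. If nobody reached 12 cycles before closure, the completer error is zero in practice; if nobody failed screening, so is the other. With few participants, each person misplaced would move a percentage noticeably. The defect does not touch the primary endpoint, which is satisfaction on the TFQ. It merits correction because the rule gives wrong counts whenever such participants exist, and because 2.3.1 still calls for a summary that SAP section 1 says will not be produced.

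**What to change.** Rewrite SAP 2.3.1 as follows:

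1. On the Enrolled Set, keep the treated/untreated row, the screening-phase disposition and the reasons for screen failure.
2. On the FAS, replace the two page-based rows with three mutually exclusive states: completed the planned 12 cycles; discontinued before the planned duration, with reason, including termination of the trial by the sponsor; and ongoing at the cut-off, expected to be 0 at LPLV.
3. Delete the 15-year follow-up row.
4. Reconcile the request for counts and percentages with the listings-only statement in SAP section 1. If only a listing is produced, show the same three states for each treated participant, and list screen failures as untreated with their reason.

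The cost is SAP and table-shell wording plus a small programming change. The data needed appear to be collected already: dosing dates, the screening disposition form and the reason for stopping treatment. The sponsor should confirm against the CRF that completion of 12 cycles can be told apart from early stopping.
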